17.5. Case Report Form Completion

Beginning with the implementation of Amendment 7, data collection through the electronic data capture (eDC) will no longer be performed.

eDC will be used for this study. Case report forms (CRF) are provided for each subject in electronic format. Study site personnel must log in eDC via a secure manner (personal password). The individual password must keep confidential for personal use.

The study data will be transcribed by study-site personnel from the source documents onto an CRF according to CRF completion guideline provided by the Sponsor. Data must be entered into CRFs in English. The CRF must be completed as soon as possible after a subject visit and the forms should be available for review at the next scheduled monitoring visit. Worksheets may be used for the capture of some data to facilitate completion of the CRF. Any such worksheets will become part of the subject's source documentation.

All subjective measurements (eg, pain scale information or other questionnaires) shall be completed by the same individual who made the initial baseline determinations whenever possible. The investigator must verify that all data entries in the CRFs are accurate and correct.

All CRF entries, corrections, and alterations must be made by the investigator or other authorized study-site personnel. If necessary, queries will be generated in the eDC tool. The investigator or study-site personnel must address the queries and update the CRF if applicable.

If necessary, queries will be generated in the eDC tool. If corrections to a CRF are needed after the initial entry into the CRF, this can be done in either of the following ways:

- Investigator and study-site personnel can make corrections in the eDC tool at their own initiative or as a response to an auto query (generated by the eDC tool).
- Sponsor or Sponsor delegate can generate a query for resolution by the investigator and study-site personnel.

17.6. Data Quality Assurance/Quality Control

Steps to be taken to ensure the accuracy and reliability of data include the selection of qualified investigators and appropriate study sites, review of protocol procedures with the investigator and study-site personnel before the study, and periodic monitoring visits by the Sponsor, and direct transmission of clinical laboratory data from a central laboratory into the Sponsor's data base. Written instructions will be provided for collection, handling, storage, and shipment of samples.

Guidelines for CRF completion will be provided and reviewed with study-site personnel before the start of the study. The Sponsor will review CRF for accuracy and completeness during on-site monitoring visits and after transmission to the Sponsor; any discrepancies will be resolved with the investigator or designee, as appropriate. After upload of the data into the study database they will be verified for accuracy and consistency with the data sources.

17.7. Record Retention

In compliance with the ICH/GCP guidelines, the investigator/institution will maintain all CRF and all source documents that support the data collected from each subject, as well as all study documents as specified in ICH/GCP Section 8, Essential Documents for the Conduct of a Clinical Trial, and all study documents as specified by the applicable regulatory requirement(s). The investigator/institution will take measures to prevent accidental or premature destruction of these documents.

Essential documents must be retained until at least 2 years after the last approval of a marketing application in an ICH region and until there are no pending or contemplated marketing applications in an ICH region or until at least 2 years have elapsed since the formal discontinuation of clinical development of the investigational product. These documents will be retained for a longer period if required by the applicable regulatory requirements or by an agreement with the Sponsor. It is the responsibility of the Sponsor to inform the investigator/institution as to when these documents no longer need to be retained.

If the responsible investigator retires, relocates, or for other reasons withdraws from the responsibility of keeping the study records, custody must be transferred to a person who will accept the responsibility. The Sponsor must be notified in writing of the name and address of the new custodian. Under no circumstance shall the investigator relocate or dispose of any study documents before having obtained written approval from the Sponsor.

If it becomes necessary for the Sponsor or the appropriate regulatory authority to review any documentation relating to this study, the investigator/institution must permit access to such reports.

17.8. Monitoring

The Sponsor will use a combination of monitoring techniques central, remote, or on-site monitoring to monitor this study.

The Sponsor will perform on-site monitoring visits as frequently as necessary. The monitor will record dates of the visits in a study site visit log that will be kept at the study site. The first postinitiation visit will be made as soon as possible after enrollment has begun. At these visits, the monitor will compare the data entered into the CRF with the source documents (eg, hospital/clinic/physician's office medical records). The nature and location of all source documents will be identified to ensure that all sources of original data required to complete the CRF are known to the Sponsor and study-site personnel and are accessible for verification by the

Sponsor study-site contact. If electronic records are maintained at the study site, the method of verification must be discussed with the study-site personnel.

Direct access to source documents (medical records) must be allowed for the purpose of verifying that the recorded data are consistent with the original source data. Findings from this review will be discussed with the study-site personnel. The Sponsor expects that, during monitoring visits, the relevant study-site personnel will be available, the source documents will be accessible, and a suitable environment will be provided for review of study-related documents. The monitor will meet with the investigator on a regular basis during the study to provide feedback on the study conduct.

In addition to on-site monitoring visits, remote contacts can occur. It is expected that during these remote contacts, study-site personnel will be available to provide an update on the progress of the study at the site. Central monitoring will take place for data identified by the Sponsor as requiring central review.

Once Amendment 6 is implemented at a site, monitoring will be limited to on-site monitoring visits and remote contacts for the verification and follow-up of SAEs reported to the Sponsor.

17.9. Study Completion/Termination

17.9.1. Study Completion/End of Study

Study completion will occur when the last subject has discontinued study treatment (atezolizumab monotherapy), completed the End of Treatment assessments, and safety follow-up has completed (ie, last required data collection for the last subject has been captured in the CRF). A CSR will be prepared based on interim analysis data reviewed by the DMC at the third planned DMC review on 23 May 2018 (prior to discontinuation of enrollment and daratumumab dosing).

The final data from the study site will be sent to the Sponsor (or designee) after completion of the final subject assessment at that study site, in the time frame specified in the Clinical Trial Agreement.

17.9.2. Study Termination

The Sponsor reserves the right to close the study site or terminate the study at any time for any reason at the sole discretion of the Sponsor. Study sites will be closed upon study completion. A study site is considered closed when all required documents and study supplies have been collected and a study-site closure visit has been performed.

The investigator may initiate study-site closure at any time, provided there is reasonable cause and sufficient notice is given in advance of the intended termination.

Reasons for the early closure of a study site by the Sponsor or investigator may include but are not limited to:

- Failure of the investigator to comply with the protocol, the requirements of the IEC/IRB or local health authorities, the Sponsor's procedures, or GCP guidelines
- Inadequate recruitment of subjects by the investigator
- Discontinuation of further study drug development.

17.10. On-Site Audits

Representatives of the Sponsor's clinical quality assurance department may visit the study site at any time during or after completion of the study to conduct an audit of the study in compliance with regulatory guidelines and company policy. These audits will require access to all study records, including source documents, for inspection. Subject privacy must, however, be respected. The investigator and study-site personnel are responsible for being present and available for consultation during routinely scheduled study-site audit visits conducted by the Sponsor or its designees.

Similar auditing procedures may also be conducted by agents of any regulatory body, either as part of a national GCP compliance program or to review the results of this study in support of a regulatory submission. The investigator should immediately notify the Sponsor if he or she has been contacted by a regulatory agency concerning an upcoming inspection.

17.11. Use of Information and Publication

All information, including but not limited to information regarding atezolizumab and daratumumab or the Sponsor's operations (eg, patent application, formulas, manufacturing processes, basic scientific data, prior clinical data, formulation information) supplied by the Sponsor to the investigator and not previously published, and any data, including exploratory biomarker research data, generated as a result of this study, are considered confidential and remain the sole property of the Sponsor. The investigator agrees to maintain this information in confidence and use this information only to accomplish this study, and will not use it for other purposes without the Sponsor's prior written consent.

The investigator understands that the information developed in the study will be used by the Sponsor in connection with the continued development of atezolizumab and daratumumab, and thus may be disclosed as required to other clinical investigators or regulatory agencies. To permit the information derived from the clinical studies to be used, the investigator is obligated to provide the Sponsor with all data obtained in the study.

The results of the study will be reported in a Clinical Study Report generated by the Sponsor and will contain data from all study sites that participated in the study as per protocol. Recruitment performance or specific expertise related to the nature and the key assessment parameters of the study will be used to determine a coordinating investigator. Results of exploratory biomarker analyses performed after the Clinical Study Report has been issued will be reported in a separate report and will not require a revision of the Clinical Study Report. Study subject identifiers will

not be used in publication of results. Any work created in connection with performance of the study and contained in the data that can benefit from copyright protection (except any publication by the investigator as provided for below) shall be the property of the Sponsor as author and owner of copyright in such work.

Consistent with Good Publication Practices and International Committee of Medical Journal Editors guidelines, the Sponsor shall have the right to publish such primary (multicenter) data and information without approval from the investigator. The investigator has the right to publish study site-specific data after the primary data are published. If an investigator wishes to publish information from the study, a copy of the manuscript must be provided to the Sponsor for review at least 60 days before submission for publication or presentation. Expedited reviews will be arranged for abstracts, poster presentations, or other materials. If requested by the Sponsor in writing, the investigator will withhold such publication for up to an additional 60 days to allow for filing of a patent application. In the event that issues arise regarding scientific integrity or regulatory compliance, the Sponsor will review these issues with the investigator. The Sponsor will not mandate modifications to scientific content and does not have the right to suppress information. For multicenter study designs and substudy approaches, secondary results generally should not be published before the primary endpoints of a study have been published. Similarly, investigators will recognize the integrity of a multicenter study by not submitting for publication data derived from the individual study site until the combined results from the completed study have been submitted for publication, within 12 months of the availability of the final data (tables, listings, graphs), or the Sponsor confirms there will be no multicenter study publication. Authorship of publications resulting from this study will be based on the guidelines on authorship, such as those described in the Uniform Requirements for Manuscripts Submitted to Biomedical Journals, which state that the named authors must have made a significant contribution to the design of the study or analysis and interpretation of the data, provided critical review of the paper, and given final approval of the final version.

Registration of Clinical Studies and Disclosure of Results

The Sponsor will register and disclose the existence of and the results of clinical studies as required by law.

REFERENCES

1. American Cancer Society; Cancer Facts and Figures 2014. Available at: <http://www.cancer.org/acs/groups/content/@research/documents/webcontent/acspc-042151.pdf>. Accessed 03 March 2015.

Attachment 1: Antihistamine Medications

The following antihistamines may be used for daratumumab preinfusion medication:

- Diphenhydramine
- Cetirizine
- Fexofenadine
- Loratadine
- Clemastine
- Dexchlorpheniramine.

Attachment 2: Conversion Table for Glucocorticosteroid Dose

Glucocorticoid	Approximate Equivalent Dose (mg)	Half-life (Biologic) hours
Intermediate-Acting		
Methylprednisolone	4	18-36
Prednisolone	5	18-36
Prednisone	5	18-36
Triamcinolone	4	18-36
Long-Acting		
Betamethasone	0.6 – 0.75	36-54
Dexamethasone	0.75	36-54

Attachment 3: ECOG Performance Status Scale

Grade	ECOG Performance Status
0	Fully active, able to carry on all pre-disease performance without restriction
1	Restricted in physically strenuous activity but ambulatory and able to carry out work of a light or sedentary nature, eg, light house work, office work
2	Ambulatory and capable of all selfcare but unable to carry out any work activities. Up and about more than 50% of waking hours
3	Capable of only limited selfcare, confined to bed or chair more than 50% of waking hours
4	Completely disabled. Cannot carry on any selfcare. Totally confined to bed or chair
5	Dead

Source: Oken 1982³⁵

Attachment 4: Anticipated Events**Anticipated Event**

An anticipated event is an adverse event (serious or non-serious) that commonly occurs as a consequence of the underlying disease or condition under investigation (disease related) or background regimen.

For the purposes of this study, the following events will be considered anticipated events:

- The clinical manifestations from primary tumors, regional spread, metastasis, and paraneoplastic syndromes will be considered as anticipated events. These events include local respiratory events (such as cough, dyspnea, hemoptysis, wheezing, chest pain, pneumonia, bronchitis, plural effusion); metastasis to nervous system events (such as bone pain, spinal cord depression, headache, seizures, meningismus, ataxia, altered mental status) and hepatic events; paraneoplastic syndromes (hypercalcemia, syndrome of inappropriate antidiuretic hormone production, Cushing syndrome).
- Given the mechanism of action of atezolizumab, events associated with immune-mediated adverse events will also be considered as anticipated events, including:
 - Pneumonitis
 - Colitis
 - Endocrinopathies (diabetes mellitus, pancreatitis, adrenal insufficiency, hyperthyroidism, hypophysitis)
 - Hepatitis
 - Transaminitis Grade ≥ 2 (AST or ALT $> 3xULN$ and bilirubin $> 2xULN$, or AST/ALT $> 10xULN$)
 - Systemic lupus erythematosus
 - Neurologic: Guillain-Barré syndrome, myasthenia gravis/myasthenic syndrome, meningoencephalitis
 - Nephritis
 - Events suggestive of hypersensitivity, cytokine release, influenza-like illness, systemic inflammatory response syndrome, systemic immune activation, infusion reactions syndrome, immune-mediated myocarditis, vasculitis, severe cutaneous adverse reactions autoimmune hemolytic anemia.

Because this is the first study of daratumumab in NSCLC subjects and with the combination of atezolizumab and daratumumab, other adverse events cannot be anticipated.

Reporting of Anticipated Events

All adverse events will be recorded in the CRF regardless of whether considered to be anticipated events and will be reported to the Sponsor as described in Section 12.3.1, All Adverse Events. Any anticipated event that meets serious adverse event criteria will be reported to the Sponsor as described in Section 12.3.2, Serious Adverse Events. These anticipated events are exempt from expedited reporting as individual single cases to Health Authorities. However, if based on an aggregate review, it is determined that an anticipated event is possibly related to study drug, the Sponsor will report these events in an expedited manner.

Statistical Analysis

Details of statistical analysis of anticipated events, including the frequency of review and threshold to trigger an aggregate analysis of anticipated events will be provided in a separate Anticipated Events Safety Monitoring Plan (ASMP).

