1. INTRODUCTION

This is an open-label, randomized, Phase 1b/2 study of the combination of 2 monoclonal antibodies, TECENTRIQ[®] (atezolizumab) and DARZALEX[®] (daratumumab) in subjects with previously treated advanced or metastatic non-small cell lung cancer (NSCLC). Both atezolizumab and daratumumab are investigational medicinal products (IMPs) in this study.

Atezolizumab is a humanized immunoglobulin G (IgG) 1 monoclonal antibody (mAb) that was engineered to target cells expressing programmed death ligand-1 (PD-L1) and inhibits its interaction with its receptor, programmed death-1 (PD-1). Atezolizumab also blocks the binding of PD-L1 to B7.1, an interaction that is reported to provide additional inhibitory signals to T cells (Butte 2007).⁷ Atezolizumab is approved by the US FDA for treatment of patients with urothelial carcinoma that has relapsed from or has become resistant to treatment with platinum-based agents (see the Product Information for atezolizumab for the specific indication). Atezolizumab is also currently approved for patients with metastatic NSCLC who have disease progression during or following platinum-containing therapy. It is currently being studied as a therapy for other solid tumors and hematologic malignancies in humans.

Daratumumab is a human immunoglobulin G1 kappa (IgG1 κ) monoclonal antibody (mAb) that binds CD38-expressing cells with high affinity. Daratumumab is approved by the US FDA for the treatment of patients with multiple myeloma who have received at least 3 lines of therapy including a proteasome inhibitor (PI) and an immunomodulatory agent (IMiD) or who are double-refractory to a PI and an IMiD; and in combination with lenalidomide and dexamethasone, or bortezomib and dexamethasone, for the treatment of patients with multiple myeloma who have received at least one prior therapy. It is also approved in the European Union for the treatment of adults with relapsed and refractory multiple myeloma (see the Product Information for daratumumab for the specific indication). It is also being studied as a therapy for other hematologic malignancies including non-Hodgkin lymphoma and amyloidosis.

For the most comprehensive nonclinical and clinical information regarding atezolizumab and daratumumab, refer to the latest versions of the respective Investigator's Brochures.

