3.3. Safety Evaluation

Dose-Limiting Toxicity (DLT)

Toxicities will be graded for severity according to the National Cancer Institute Common Terminology Criteria for Adverse Events (NCI-CTCAE), Version 4.03. During the 6-subject Safety Run-in phase, the DLT evaluation period is 21 days starting from the day of the first dose of study drug. Only toxicities that occur during the DLT evaluation period will be considered for DLT assessment. Subjects who are not evaluable for DLT can be replaced. A DLT evaluable subject (DLT evaluable analysis set) is:

- Any subject who has a DLT regardless of dose received or
- A subject who did not have a DLT but received at least 75% of the planned dose during the DLT evaluation period.

Dose-limiting toxicity is defined as any of the events listed in Table 6. Toxicities with a clear alternative explanation (eg, due to disease progression) or transient toxicities (≤ 72 hours) and abnormal laboratory values without associated clinically significant signs or symptoms based on investigator determination can be deemed a non-DLT.

Table 6: Criteria for Dose-limiting Toxicity

DLT criteria for Non-hematologic Toxicity^a	
AST or ALT	Grade 3 persisting ≥ 14 days after treatment with corticosteroids, Grade 4, or any case meeting Hy's Law criteria ^b
Laboratory abnormality	Grade 3 persisting ≥ 7 days despite BSC ^c or Grade 4
Any other^d	Grade 3 persisting ≥ 7 days despite BSC ^c or Grade 4; except Grade ≥ 3 asymptomatic or mildly symptomatic rash that can be adequately managed with supportive care or resolves to become asymptomatic or Grade ≤ 2 within 7 days of supportive therapy.
Infusion-related reaction	Grade 4 infusion-related reaction that occurs during or within 24 hours after the infusion of atezolizumab or daratumumab.
Ocular toxicity	Grade 2 or higher episcleritis, uveitis, or iritis
DLT criteria for Hematologic Toxicity^a	
Neutropenia	Grade 3 persisting > 7 days despite BSC ^c , febrile neutropenia, or any Grade 4
Thrombocytopenia	Grade 3 with bleeding or Grade 3 persisting > 7 days despite BSC ^c , or any Grade 4
Any other	Grade 3 persisting ≥ 7 days despite BSC ^c or Grade 4

ALT=alanine aminotransferase, AST=aspartate aminotransferase, ALP=alkaline phosphatase

- Toxicity graded according to the NCI-CTCAE, Version 4.03.
- Hy's Law criteria, defined as ALT or AST value ≥ 3 x upper limit of normal (ULN), total bilirubin ≥ 2 x ULN, and ALP ≤ 2 x ULN; with no alternative etiology.

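### Attachment 4 exempts atezolizumab's immune-mediated and infusion-type events from individual expedited reporting, outside its own definition of an anticipated event and against the rule in Section 12.1.1

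*Protocol*

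**What the plan says.** Protocol Attachment 4 defines an anticipated event as an adverse event, serious or not, that "commonly occurs as a consequence of the underlying disease or condition under investigation (disease related) or background regimen". The first bullet lists manifestations of lung cancer. The second rests on a different ground: "Given the mechanism of action of atezolizumab, events associated with immune-mediated adverse events will also be considered as anticipated events". Its entries include pneumonitis, colitis, endocrinopathies, hepatitis, nephritis, Guillain-Barré syndrome, myasthenia gravis, meningoencephalitis, myocarditis, systemic immune activation and infusion reactions. A line opening "Transaminitis Grade" ≥2 adds AST or ALT above 3×ULN with bilirubin above 2×ULN, or AST/ALT above 10×ULN.

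The consequence follows under Reporting of Anticipated Events: "These anticipated events are exempt from expedited reporting as individual single cases to Health Authorities". The sponsor does expedite "if based on an aggregate review, it is determined that an anticipated event is possibly related to study drug". How often that review takes place, and what triggers it, is left to a separate Anticipated Events Safety Monitoring Plan (ASMP).

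On the status of the drugs, Section 1 states: "Both atezolizumab and daratumumab are investigational medicinal products (IMPs) in this study". Section 12.1.1 obliges the sponsor to report a serious, unexpected event with evidence of causality as a suspected adverse reaction, even when the event is part of a study endpoint. Expectedness there depends on nature and severity, judged against the Reference Safety Information in the Investigator's Brochures.

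**The concern.** An anticipated-event exemption makes sense for disease events. They are frequent in this population, a single case says little about the drug, and only a comparison of rates is informative. The events in the second bullet are on the list for the opposite reason: a study drug is expected to cause them. For these a single well-documented case can be informative, above all if it is more severe than the reference information describes.

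At stake is the route of one kind of case: serious, suspected to be caused by a study drug, and unlisted. Section 12.1.1 sends it to expedited reporting. Attachment 4, read as written, lets it wait for an aggregate review whose timing these documents do not give.

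**Working it through.** No sample size, power or event count bears on this point. The check sets the provisions side by side.

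**1. Do the added events meet the definition?** It has two limbs.
- *Disease.* The second bullet invokes the drug's mechanism, not the disease.
- *Background regimen.* No section gives atezolizumab that status, and Section 1 names it as investigational.

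The definition also asks that the event occur commonly. Section 1.2 reports, among 609 atezolizumab patients in the Phase 3 study, pneumonitis in 6 (6/609 = 1.0%), Grade 3 hepatitis in 2 and Grade 2 colitis in 2 (2/609 = 0.3% each). Sections 6.2.1.11 and 6.2.1.12 describe nephritis as relatively rare and systemic immune activation as rare.

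**2. Is the bullet confined to atezolizumab?** No. The infusion-reaction entry names no drug. Section 1.4 puts infusion reactions at about half of daratumumab patients and about 1% of atezolizumab patients, so the entry reaches daratumumab. Section 6.2.1.12 treats systemic immune activation as a potential risk when atezolizumab is combined with other immunomodulating agents. That is a risk of a combination, not of a background drug alone.

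**3. Which cases change route?**

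| Serious, drug-suspected case | Section 12.1.1 | Attachment 4 |
|---|---|---|
| Listed in nature and severity | Not unexpected, so this rule does not require a report | Exempt: no change under this rule |
| Unlisted in nature or severity | Must be reported as a suspected adverse reaction | Exempt as an individual case: conflict |

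The conflict lies in the second row.

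**4. How does the liver entry compare with Table 6?** Table 6 makes "any case meeting Hy's Law criteria" a dose-limiting toxicity. Its footnote b sets out the "Hy's Law criteria, defined as ALT or AST value" of at least 3×ULN, with the further conditions below. I take the thresholds in Attachment 4's parentheses as defining that line.

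| Condition | Table 6, footnote b | Attachment 4 |
|---|---|---|
| ALT or AST | ≥3×ULN | >3×ULN |
| Bilirubin | ≥2×ULN | >2×ULN |
| ALP | ≤2×ULN | none |
| Etiology | no alternative | none |
| Other way in | none | AST/ALT >10×ULN |

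Every Table 6 case falls inside the exempt line, apart from values exactly at 3×ULN or 2×ULN with AST/ALT not above 10×ULN. The exempt line is also wider, because it drops the ALP and etiology conditions.

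**5. Does the aggregate-review safeguard close the gap?** Only partly. It lifts the exemption once a possible relation to study drug is found across cases. Events in the second bullet are there because that relation is already presumed, so the trigger restates the reason for listing them. It also acts after accumulation, whereas the Section 12.1.1 rule attaches to the single case.

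**The case against.** The best defense is that atezolizumab works as background. Both arms receive it (Section 16.1), and Section 1 notes its approval in metastatic NSCLC after platinum. Whether daratumumab worsens immune-mediated toxicity is a between-arm question, which aggregate data answer better than one case. The third DMC review made such a comparison and saw no unexpected imbalance in on-treatment toxicity (Section 1.4). This explains what the sponsor may have intended. It does not remove the defect: the protocol never assigns that status, and the exemption as written still catches unlisted cases suspected to be caused by a study drug.

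Several limits do stand.
- **Safeguards remain.** Serious events go to the sponsor within 24 hours (Section 12.3.2). For serious anticipated events the sponsor judges relatedness independently of the investigator and evaluates accumulating data periodically (Section 12.3.1).
- **Section 12.3.1 is not contradicted.** A reader might infer a conflict with it too, but it adopts Attachment 4 and describes this separate route. The conflict is with Section 12.1.1.
- **A count of classes would mislead.** Matching headings puts 10 of the 11 toxicity tables in Attachment 7 on the list, all but ocular events. The contents do not match. Attachment 4 does not name hypothyroidism, isolated amylase or lipase elevation, Grade 1 or 2 dermatologic events, or immune-related neuropathy. Nor does the count say how many reports are affected.
- **Hy's Law as such is not listed.** Attachment 4 does not use the term. Table 6 governs dose-limiting toxicity in the six run-in subjects over 21 days, and that status does not decide expedited reporting.
- **The combination has stopped.** Daratumumab is discontinued and crossover closed (Sections 3.2 and 6), so the forward-looking exposure is atezolizumab monotherapy.

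**Conclusion.** The point holds as an internal contradiction in safety reporting. The second bullet of Attachment 4 falls outside the attachment's own definition. The exemption attached to it conflicts with Section 12.1.1 for serious, unlisted cases with evidence of causality.

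Its size is unknown. It depends on which events and severities the Reference Safety Information lists, and on the review schedule in the ASMP; neither is among these documents. A reader might infer that reportable cases have been held back. Nothing here shows that even one was, and Section 12.1.1 can be read as still governing such a case. The documents do not say which provision prevails, and that is the gap to close.

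It is still worth closing after the DMC decision. Since Amendment 7, serious adverse events are the only safety data collected from continuing subjects (Sections 9.3 and 12.5), and serious events from the combination period were received under the same wording.

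**What to change.** Make one of two changes in Attachment 4:
- remove the second bullet from the list of events exempt from individual expedited reporting; or
- add to the reporting paragraph that the exemption does not apply to any serious event that is suspected to be related to either study drug and is unlisted under Section 12.1.1.

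The second option leaves the list intact and settles which rule prevails. With either one, align Section 12.3.1 and the ASMP, and keep aggregate monitoring of these events as an addition to individual reporting. Then check once whether any serious adverse event already received was not expedited because of the exemption. The check may find none.

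The cost is protocol and ASMP wording, that one review, and possibly a few more individual case reports. Treatment, assessments and planned analyses do not change.
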